14.1 Appendix A. Handling of Dates, Incomplete Dates and Missing Dates

Imputation Rules for Partial or Missing Start Dates

The reference date for the following rules is the date of first dose of AMG 910.

Start Date		Stop Date						
		Complete: yyyymmdd		Partial: yyyymm		Partial: yyyy		Missing
		< 1 st dose	≥ 1 st dose	< 1 st dose	≥ 1 st dose	< 1 st dose	≥ 1 st dose	
Partial: yyyymm	= 1 st dose yyyymm	2	1	n/a	1	n/a	1	1
	≠ 1 st dose yyyymm		2	2	2	2	2	2
Partial: yyyy	= 1 st dose yyyy	3	1	3	1	n/a	1	1
	≠ 1 st dose yyyy		3		3	3	3	3
Missing		4	1	4	1	4	1	1

1=Impute the date of first dose; 2=Impute the first of the month; 3=Impute January 1 of the year; 4=Impute January 1 of the stop year

Note: For subjects who were never treated (first dose date is missing), partial start dates will be set to the first day of the partial month or first day of year if month is also missing.

Imputation Rules for Partial or Missing Stop Dates

Initial imputation

- If the month and year are present, impute the last day of that month.
- If only the year is present, impute December 31 of that year.
- If the stop date is entirely missing, assume the event or medication is ongoing.

If the imputed stop date is before the start date, set stop date to missing.

If the imputed stop date is after the death date, impute as death date.

Imputation Rules for Partial or Missing Death Dates

If death year and month are available but day is missing:

- If yyyyymm for the date last known to be alive equals yyyyymm for death date, set death date to the day after the date last known to be alive.
- If yyyyymm for the date last known to be alive is less than the yyyyymm for death date, set death date to the first day of the death month.

- If yyyyymm for the date last known to be alive is greater than yyyyymm for death date, assume death date is in error, do not impute and censor the subject survival time.

If month and day are missing and year of death is known:

- If yyyy for the date last known to be alive equals yyyy for death date, set death date to the day after last known to be alive date.
- If yyyy for the date last known to be alive is less than yyyy for death date, set death date to the first day of the death year.
- If yyyy for the date last known to be alive is greater than yyyy for death date, assume death date is in error, do not impute and censor the subject survival time.

If a death date is totally missing:

Do not impute and censor the subject survival time.

14.2 Appendix B. RECIST (v1.1) Criteria

BOR will need to be derived based on timepoint response collected on RECIST 1.1 CRF.

Table 14-1 provides the BOR determination per RECIST 1.1 for trials where response confirmation is required. That means in the case of confirming CR or PR, a confirmation is required by a repeat assessment at least 4 weeks after the first detection and assessments of NE may occur between timepoint T1 and timepoint T2. For example, BL, CR, NE, NE, NE, CR – then CR at post baseline 1 is confirmed at post baseline 5. A BOR determined by **Table 14-1** is considered a **Confirmed_BOR**. At interim analysis, an unconfirmed response rate may be reported in addition to the confirmed response rate. The unconfirmed rate includes subjects who achieved a PR or CR and are awaiting a confirmative scan (i.e., unconfirmed responders). If these subjects have disease progression or death before the confirmative scan, then they are no longer considered as unconfirmed responder awaiting confirmative scan. Timepoint response “NON-CR/NON-PD” will be considered as “SD” in the algorithm of confirmation. **Interim_BOR** is defined to include these subjects in addition to **Confirmed_BOR**. **Table 14-2** outlines the steps to derive **Confirmed_BOR** and **Interim_BOR** given the timepoint assessments.

Table 14-1. BOR per RECIST 1.1

Criterion	Timepoint T1 Response	T1 ≥ 35* days after Baseline?	Timepoint T2 Response	T2 ≥ 35* days after Baseline?	T2 ≥ 28 days after T1?	BOR at time point T1
C1	CR	Yes	CR	-	Yes	CR
C2			CR	-	No	SD
C3			PR, SD	-	-	Query data**
C4			PD	-	-	SD
C5			NE, No further evaluations			SD
C6		No	CR	-	Yes	CR

C7		CR	Yes	No	SD	
C8		PR, SD	-	-	Query data**	
C9		PD	-	-	PD	
C10		NE, No further evaluations			NE	
C11	PR	Yes	CR, PR	-	Yes	PR
C12			CR, PR	-	No	SD
C13			SD	-	-	SD
C14			PD	-	-	SD
C15			NE, No further evaluations			SD
C16		No	CR, PR	-	Yes	PR
C17			CR, PR	Yes	No	SD
C18			SD	Yes	-	SD
C19			PD	-	-	PD
C20			NE, No further evaluations			NE
C21	SD	Yes	CR, PR, SD, PD, NE, no more evaluation		SD	
C22		No	CR, PR, SD	Yes	-	SD
C23			CR, PR, SD	No	-	NE
C24			PD	-	-	PD
C25			NE, No further evaluations			NE
C26	PD		-			PD
C27	NE	-	NE, No further evaluations			NE
C28		-	CR, PR, SD	Yes	-	SD
C29		-	CR, PR, SD	No	-	NE
C30		-	PD	-	-	PD

CR= complete response, PR= partial response, SD= stable disease, PD= progressive disease, and NE= not evaluable.

*CR and PR need to be confirmed, which requires a repeat assessment at least 4 weeks after the first detection. Notice an unlimited number of intermittent assessments of NE can occur between the initial response and the confirmation. For example, CR, NE, NE, NE, CR – then CR at post baseline 1 is confirmed at post baseline 5. Both first detection and repeat assessment can be unscheduled visit and the 4 weeks apart rule needs to be met. For SD, a duration of at least 6 weeks after baseline scan is required. The threshold of 35 days accounts for the earliest available assessment by RECIST 1.1, as for tumor assessment per scheduling of imaging assessment.

**If a CR is truly met at timepoint T1, then any disease seen at a subsequent time point, even disease meeting PR criteria relative to baseline, makes progressive disease at that time point (i.e., disease must have re-appeared after CR). Best overall response would depend on whether minimum duration for SD was met. However, sometimes 'CR' may be claimed when subsequent scans suggest small lesions were likely still present and in fact the patient had PR, not CR at timepoint T1. Under this circumstances, the original CR should be changed to PR and the best response is PR.

Table 14-2. BOR Derivation Steps for GSP

Step 1. Derive Confirmed_BOR at each visit
Derive Confirmed_BOR at each visit:

 At Visit 1: Using the Visit 1 scan result and refer to Table 14-1 to derive Confirmed_BOR. At Visit 2 onward:

- (a) If current visit is CR or PR: Find last scan that is not NE or SD and at least 28 days before current visit. Derive *BOR_temp* as below:

Last scan	Current	BOR_temp
CR	CR	CR
PR	CR	PR
PR	PR	PR

- (b) If none of above fits, find last scan that is not NE, reference [Table 14-1](#) to derive *BOR_temp*.
- iii) Current visit *Confirmed_BOR* = best of (*BOR_temp*, last visit *confirmed_BOR*). Use rule CR > PR > SD > PD > NE

Step 2. Derive *Interim_BOR* at last visit prior to analysis data cutoff

For subjects who discontinue tumor assessment (ie, had PD, death, next therapy, withdraw consent, or end of study): Assign Interim_BOR = Confirmed_BOR	For subjects with potential for more assessment (ie, no PD, death, next therapy, withdraw consent, or end of study), unconfirmed PR/CR can be considered responders. 
• If any scan is CR and no PD/death, then Interim_BOR = CR.• If any scan is PR and no CR or PD/death, then Interim_BOR = PR.• Else, Interim_BOR = Confirmed_BOR at the latest scan.
---	--

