^b For subjects who discontinued treatment for any reason other than confirmed disease progression, every effort should be made to perform radiographic imaging (CT) of the chest, abdomen, pelvis, and all other known sites of disease every 3 months until documentation of confirmed disease progression per RECIST 1.1 and iRECIST, clinical progression, start of new anticancer therapy, or up to 2 years after the first dose of AMG 910, whichever occurs first.

Notes: If CT and/or MRI is done prior to ICF signature results can be used if the subjects allows its use and assessments are done within 30 days of C1 day 1, as outlined in Section 8.1.1.

There is a tolerability window of \pm 1 week for the imaging assessments.

2. Introduction

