8.2.2 Efficacy Assessments

Efficacy will be determined by both clinical laboratory values and radiographic assessments (as outlined in Section [3](#)).

Radiographic Assessments

Radiographic assessments will be obtained as scheduled in [Table 1-3](#) irrespective of cycle duration including dose delays and treatment discontinuation. Standard radiological assessments should take place until clinically significant disease progression or deterioration, withdrawal of consent, or start of new anticancer therapy. Every assessment must include contrast-enhanced CT of the chest, abdomen, pelvis, and all other known sites of disease. The assessment should include MRI of the brain if a subject has signs or symptoms suggestive of CNS metastases. The assessment can be conducted earlier if clinical deterioration necessitates an earlier scan at the discretion of the managing physician. The same contrast and modality used at screening should be used for all subsequent assessments.

Tumor burden assessments will be performed based on RECIST 1.1 and iRECIST. RECIST 1.1 criteria will be used to determine eligibility based on the investigator's review of the radiographic data. Although tumor assessments following RECIST 1.1 will continue through the first disease progression (PD), iRECIST will be used and documented in eCRF to account for unique tumor response characteristics observed with immunotherapies and enable treatment decisions beyond progression (per RECIST 1.1). Tumor burden assessment performed at sites for decisions on treatment continuation will be based on iRECIST only and will continue until immune Confirmed Progression Disease (iCPD). Tumor burden assessments by the central core laboratory will be based on RECIST 1.1 and iRECIST. To confirm disease progression, a second CT scan must be performed 4-8 weeks after the first detection of radiographical progression. Responses (partial response [PR] and complete response [CR]) require confirmation by a repeat consecutive assessment at least 4 weeks after the first detection of radiographical response. Refer to the imaging manual for details on imaging assessments.

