4.2 Subgroups

Not applicable.

5. Definitions

Adverse events

An adverse event (**AE**) is any untoward medical occurrence in a clinical study subject irrespective of a causal relationship with the study treatment.

Age at enrollment

Subject age at enrollment will be determined using the age in years reported in the clinical database.

Area under the Curve (AUC)

The area under the **serum** drug concentration-time curve (AUC) reflects the actual body exposure to drug after administration of a dose of the drug.

Baseline

For any variable, unless otherwise specified, the baseline is the last non-missing assessment taken prior to the first administration of AMG 910.

For parameters/assessments not scheduled to be performed (or scheduled but not performed) on the same day as the first administration of AMG 910, the baseline value is the value from the screening period measured closest to the day of first administration of AMG 910.

Baseline ECG values in triplicate

The mean of values in a triplicate should be calculated for Baseline. Baseline triplicate value is the mean of all pre-dose assessments. For all post- baseline ECG, the mean value for measurements taken at the same assessment will be calculated and used in the analysis.

When an ECG is missing within a triplicate, all available data will be averaged for that time point.

Best Overall Response (BOR) - using RECIST v1.1 criteria

BOR is defined as the best response in the following order: CR, PR, SD, PD, or NE, where CR and PR require confirmation by a repeat consecutive assessment at least 4 weeks after the first detection of radiographical response or progressive disease. Confirmation of SD, minimum 6 weeks duration from the baseline scan is required. The details of derivation of BOR is described in [Appendix B](#).

Complete response (CR) per RECIST v1.1 criteria

Disappearance of all target lesions, non-target lesions and normalization of tumor markers. Any pathological lymph nodes (whether target or non-target) must have reduction in short axis to <10 mm.

Objective Response Rate (ORR) per RECIST v1.1 criteria

Objective response rate is defined as the proportion of patients with a BOR of CR or PR.

Partial Response (PR) per RECIST v1.1 criteria

Partial Response (PR) is defined as at least a 30% decrease in the sum of diameters of target lesions, taking as reference the baseline sum diameters. Non target lesions must be non-Progressive Disease (non-PD).

BMI

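### Stable disease is tested at 35 days from the baseline scan, but the 35 days come from a scan schedule that most naturally starts at first dose, so up to 30 untreated days count towards it

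*SAP*

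**What the plan says.** **Minimum duration in the text.** The best overall response (BOR) definition in SAP Section 5 states: "Confirmation of SD, minimum 6 weeks duration from the baseline scan is required". The Appendix B footnote repeats it and then turns to the table's number: "For SD, a duration of at least 6 weeks after baseline scan is required. The threshold of 35 days".

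**Minimum duration in the table.** In SAP Table 14-1 the first timing column asks whether "T1 ≥ 35* days after Baseline", and the column for the second time point uses the same number. The footnote gives the reason: "The threshold of 35 days accounts for the earliest available assessment by RECIST 1.1, as for tumor assessment per scheduling of imaging assessment".

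**Imaging schedule.** Protocol Table 1-3 asks for 6-weekly CT up to week 12, with a window of plus or minus "1 week for the imaging assessments". It does not state the day from which the 6 weeks run. Protocol Section 8.1.2 makes the first dose day 1 and schedules later visits from it.

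**Age of the baseline scan.** The notes to Table 1-3 and Protocol Section 8.1.1 accept a scan taken before consent if "assessments are done within 30 days of C1 day 1", and the study schema note (Section 1.2) gives the same 30 days for screening scans generally. Protocol Appendix 11 allows 4 weeks. The default screening window is 21 days.

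**Scans outside the schedule.** Protocol Section 8.2.2 says: "The assessment can be conducted earlier if clinical deterioration necessitates an earlier scan at the discretion of the managing physician". Table 1-3 also requires a CT at the end-of-treatment or safety follow-up visit when none was done in the previous 8 weeks.

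**The concern.** A minimum duration for stable disease (SD) is meant to stop a single early scan from counting as disease control. The footnote's reasoning fits that purpose if 35 days is the earliest in-window scan on treatment. The table applies the number to a different clock. Counted from the baseline scan, some or most of the 35 days can pass before any drug is given, and how many depends on how old the baseline scan happens to be.

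What is at stake is the BOR table in SAP Section 9.5.2. A subject who is stable on a very early scan and progresses at the next one would be shown as SD rather than progressive disease (PD). A subject with no later evaluable scan would be shown as SD rather than not evaluable (NE). In addition, Section 5 and Table 14-1 can give different answers for the same scan, so two programmers could produce different tables.

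**Working it through.** **1. The SAP's 35 days.** First scheduled scan minus the window: 6 × 7 − 7 = 35 days. This reproduces the threshold and agrees with the footnote's explanation.

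**2. Earliest day after first dose on which the SD rule can be met.** Let *a* be the age of the baseline scan, in days, at first dose. Counted from the baseline scan, the earliest day is the threshold minus *a*.

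| *a* (source) | 35 days from baseline scan | 42 days from baseline scan | 35 days from first dose |
|---|---|---|---|
| 0 | 35 | 42 | 35 |
| 21 (screening window) | 14 | 21 | 35 |
| 28 (Appendix 11) | 7 | 14 | 35 |
| 30 (schema; Table 1-3 notes) | 5 | 12 | 35 |

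Replacing 35 by 42 moves each entry by only 7 days. The starting point matters more.

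**3. What Table 14-1 then assigns.** The middle columns show the result when the first scan does or does not pass the 35-day test.

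| First read, then next | Passes | Fails |
|---|---|---|
| SD, then PD | SD (C21) | PD (C24) |
| SD, then NE or nothing | SD (C21) | NE (C25) |
| PR, then PD | SD (C14) | PD (C19) |
| PR, then NE or nothing | SD (C15) | NE (C20) |
| PR, confirmed at 28 days or more | PR (C11) | PR (C16) |
| CR, confirmed at 28 days or more | CR (C1) | CR (C6) |

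An unconfirmed CR behaves like the unconfirmed PR (C4 and C5 against C9 and C10). A PD read on the first scan is PD whatever its date (C26). Step iii of Table 14-2 keeps the better of the current and previous result, ranking SD above PD and NE, so an SD once assigned is not lost.

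Example: baseline 30 days before dosing, SD read 5 days after first dose, PD at week 6. The first scan is 30 + 5 = 35 days after baseline, so C21 gives SD. Counted from first dose, 5 is less than 35 and C24 gives PD.

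**4. A required scan can have the same effect.** The end-of-treatment or follow-up CT is triggered when more than 8 × 7 = 56 days have passed since the last scan.

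- *a* = 30: a visit 27 days after first dose is 57 days after baseline. The CT is required and passes the test before day 35.
- *a* = 28: the same happens from day 29 (28 + 29 = 57).
- *a* = 21: the trigger is not reached until day 36 (21 + 36 = 57), so this route is closed.

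**5. Where text and table disagree on a scheduled scan.** A scan 35 days after first dose is 35 + *a* days after baseline. It always passes the table's test. It falls short of 42 days when *a* is 0 to 6. With *a* = 3, 38 days have elapsed: SD by Table 14-1, not SD by Section 5.

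**6. Size per subject.** 1/3 = 33 points, 1/4 = 25 points, 1/36 = 2.8 points.

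**The case against.** The strongest case for leaving the rule alone has four parts.

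- *The 35 days are explained.* This stands. A reader might infer a bare contradiction between 6 weeks and 35 days, but the footnote presents 35 days as the windowed form of 6 weeks. What remains is that Section 5 does not carry the allowance and so conflicts with the table in the cases of step 5.
- *The baseline scan is the stated starting point in all three places.* This is true, and nothing in the documents says SD should be counted from first dose. But the reason given for the number is the imaging schedule, and that reason holds only if both start on the same day. The first-dose origin of the schedule is itself inferred from Protocol Section 8.1.2.
- *Day 5 is a corner case.* This also stands. It needs the oldest permitted baseline scan and an off-schedule scan for deterioration that is nevertheless read as SD or better. A reader might infer that a subject already progressing on that scan would be called SD. The documents do not support this, because C26 gives PD. The footnote's sentence admitting unscheduled visits concerns CR and PR; for SD one can say only that the tables do not exclude them.
- *No decision depends on it.* This stands. SD rate is not a listed endpoint, response rate counts only CR and PR, futility uses objective response, and the MTD uses DLTs. A reader might infer an inflated response rate, but rows C1/C6 and C11/C16 show that confirmed responses do not depend on the 35-day test.

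**Conclusion.** The point holds as a mismatch of starting points, together with a smaller inconsistency between SAP Section 5 and Table 14-1. Time before treatment counts towards SD, so the rule can be met from 5 days after first dose at the 30-day limit, 7 days at 4 weeks and 14 days at 21 days. A required end-of-treatment or follow-up scan can meet it before day 35 when the baseline scan is at least 57 − 34 = 23 days old. Later progression does not reverse the result.

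The consequence is confined to the descriptive split between SD, PD and NE. If that split is shown by dose level, one affected subject moves 25 to 33 points in a cohort of 3 or 4. The 2.8 points at the planned expansion size of 36 are only illustrative, since SAP Section 7.1 reports early termination. The number of affected subjects cannot be estimated, because the documents do not give the frequency of early scans or the distribution of baseline-scan ages. The conclusion assumes that the 6-weekly schedule starts at first dose.

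**What to change.** Use one threshold and one starting point in the SAP Section 5 definition, in both timing columns of Table 14-1 and in the footnote: the scan date must be at least 35 days (6 weeks minus the 1-week window) after the date of the first dose of AMG 910. Write it as a difference of dates, because the SAP's study-day formula adds 1. Add NE to the categories tabulated in SAP Section 9.5.2, which now lists only CR, PR, SD and PD.

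The cost is SAP wording and one date variable in the BOR program. Every in-window scheduled scan during treatment still passes, on the stated assumption about the schedule. The SD proportion may fall slightly, with affected subjects moving to PD (C24, C19) or NE (C25, C20). The age of the baseline scan would then no longer affect this rule, although the 30-day, 4-week and 21-day limits should still be reconciled.

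### The footnote for a doubtful CR sets best response to PR with no confirmation condition, so in a few rare scan sequences the SAP gives two answers, PR and SD

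*SAP*

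**What the plan says.** **The footnote.** Table 14-1 (SAP Section 14.2, Appendix B) derives best overall response from pairs of scans, T1 and T2. Rows C3 and C8 cover T1 = CR with T2 = PR or SD. Their column for a gap of at least 28 days holds a dash, so no gap is required. Their result is a data query marked **, and footnote ** then distinguishes two cases. If the CR was real, any later disease is progression and best response depends on the minimum duration for SD. The other case is that "sometimes 'CR' may be claimed when subsequent scans suggest small lesions were likely still present and in fact the patient had PR, not CR". For that case: "Under this circumstances, the original CR should be changed to PR and the best response is PR".

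**The confirmation rule.** It appears in four places:
- the opening text of Appendix B: "in the case of confirming CR or PR, a confirmation is required by a repeat assessment at least 4 weeks after the first detection";
- footnote * to Table 14-1: "CR and PR need to be confirmed, which requires a repeat assessment at least 4 weeks after the first detection";
- the best overall response definition in SAP Section 5: "CR and PR require confirmation by a repeat consecutive assessment at least 4 weeks after the first detection of radiographical response";
- protocol Section 8.2.2, where PR and CR "require confirmation by a repeat consecutive assessment at least 4 weeks after the first detection of radiographical response".

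**How the result is used.** Appendix B labels a best response taken from Table 14-1 Confirmed_BOR and keeps a separate Interim_BOR for responses still awaiting confirmation. SAP Section 5 counts a best response of CR or PR as an objective response. Section 9.5.2 tabulates the proportion by planned dose level with a 95% CI.

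**The concern.** Once T1 has been relabelled PR, the sequence is PR then PR, or PR then SD. Table 14-1 already classifies both, and it gives PR only when a second PR or CR follows at least 28 days later. The footnote skips that test and states the answer. Its marker sits on a cell that includes SD, and even for PR it sets no minimum gap.

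Two programmers could therefore derive different best responses from the same scans. Where they differ, the footnote's answer is the higher one and enters Confirmed_BOR, the category meant to exclude unconfirmed responses. Response is reported by dose level in cohorts planned at 3 to 4 subjects, where a single reclassified subject is visible.

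**Working it through.** **1. The plan's own figure.** SAP Section 3.2 gives a 95% CI of 8% to 36% for a 19% response rate in 36 subjects. The Clopper-Pearson limits for x responders among n are the 0.025 quantile of Beta(x, n − x + 1) and the 0.975 quantile of Beta(x + 1, n − x). For 7/36 = 19.4% they are 8.2% and 36.0%, so the stated interval reproduces.

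**2. Footnote against table.** Relabel T1 as PR and read the PR rows:

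| T2 | Gap T1 to T2 | Footnote ** | PR rows of Table 14-1 |
|---|---|---|---|
| PR | at least 28 days | PR | PR (C11, C16) |
| PR | under 28 days | PR | SD (C12; C17 if T1 is before day 35) |
| SD | any | PR | SD (C13; C18 if T1 is before day 35) |

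Rows C17 and C18 also require T2 to be at least 35 days after baseline. Rows C11 to C20 have no entry for PR then SD, or PR then CR/PR under 28 days later, when T2 is before day 35.

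**3. Test patterns.** Sixteen C3/C8 patterns were run: T1 on day 28 or 42; T2 = PR or SD; gap 14, 27, 28 or 42 days. The footnote gives PR in 16 of 16. The PR rows give PR in 4 (T2 = PR with a gap of 28 or 42 days) and SD in 12. These patterns exercise the rule and say nothing about frequency.

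**4. Route through Table 14-2.** With T1 still entered as CR, a CR-then-PR pair is not in the step (a) lookup. It falls to step (b), which refers back to Table 14-1 and so to the footnote. With T1 corrected to PR:
- PR then PR at 28 days or more is PR under step (a).
- The other two sequences fall to step (b) and give SD.
- PR, SD, PR with the two PRs at least 28 days apart is a confirmed PR, because step (a) passes over an intervening SD.

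**5. Can the sequences occur?** Protocol Table 1-3 schedules scans every 6 weeks for 12 weeks, then every 8 weeks, each ± 1 week.
- Week 6 late to week 12 early: (84 − 7) − (42 + 7) = 77 − 49 = 28 days.
- Week 12 late to week 20 early: (140 − 7) − (84 + 7) = 133 − 91 = 42 days.

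A gap under 28 days therefore needs an unscheduled scan, which footnote * allows. CR then SD needs none. As an illustration, take a lone target node of 15 mm, then 9.9 mm, then 11 mm. The second value is below the 10 mm limit for CR and is a fall of (15 − 9.9)/15 = 34%, enough for PR. The third is a fall of (15 − 11)/15 = 26.7% from baseline, short of the 30% for PR. It is also a rise of only 1.1 mm (11%), short of the 20% and 5 mm for progression in protocol Table 11-9. It is SD.

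**6. Effect of one such subject** (Clopper-Pearson 95% CI):

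| Denominator | Confirmation applied | Footnote applied |
|---|---|---|
| 4 | 0/4 = 0% (0 to 60.2%) | 1/4 = 25% (0.6 to 80.6%) |
| 36 | 7/36 = 19.4% (8.2 to 36.0%) | 8/36 = 22.2% (10.1 to 39.2%) |

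**The case against.** The strongest reply is that the output of rows C3 and C8 is a query, not a PR. The footnote tells the reader to correct the timepoint, best response is derived from timepoint responses on the CRF, and footnote * directly above insists on the four-week rule. A programmer who corrects T1 and re-runs Table 14-2 gets SD for an unconfirmed case. On that reading the footnote merely ends on a loose clause.

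Much of this stands. A reader might infer that the SAP always counts an unconfirmed response as a confirmed responder. The documents do not support that, because the re-run route is open and gives the right answer. But the footnote names the resulting best response instead of calling for a re-run, and nothing says which takes precedence.

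A second reply is that the footnote's scenario, small residual lesions, suits T2 = PR much better than T2 = SD. With a 30 mm baseline sum, T2 as SD means more than 0.70 × 30 = 21 mm. To avoid a 5 mm rise, T1 must then exceed 21 − 5 = 16 mm, which is hardly a CR misread. This also stands: CR then SD is plausible only near the size limits, as in the node example. It makes the case rare, not impossible. For scheduled CR-then-PR scans the footnote's answer is correct.

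**Conclusion.** The wording is internally inconsistent, and the point is **minor**. The footnote agrees with the rest of the plan when T2 is PR at least 28 days after T1. It conflicts when T2 is SD, or is PR sooner than 28 days. For those sequences the same scans yield PR or SD according to which instruction is followed, and the difference can only raise the confirmed response rate.

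A reader might take two conflicting sequences out of three, or 12 patterns out of 16, as a measure of how often the result is wrong. They count branches of a rule, not subjects. The documents give no count of CR-then-PR or CR-then-SD subjects, and it is probably very small. The one-subject shifts are hypothetical, and 36 is the planned expansion size, whereas SAP Section 7.1 records that the study was terminated early. The combined final analysis is still planned, so the derivation still has to be unambiguous. Response is secondary and descriptive, and no sample-size figure changes.

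**What to change.** In footnote **, keep the instruction to change the CR to PR and replace the closing clause that assigns the best response with:

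*and Confirmed_BOR is re-derived from the corrected timepoint sequence using Tables 14-1 and 14-2, so that PR is assigned only if a PR or CR at least 28 days later confirms it.*

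Table 14-2 needs to be named. Rows C11 to C20 alone would miss a PR confirmed across an intervening SD, and they have no entry for the early-T2 cases noted in the working.

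The cost is one clause in the SAP and no new data. The reported response rate could be slightly lower if any such subject exists.

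### SAP Table 14-2 step ii(a) skips an intervening SD, so PR-SD-PR or PR-SD-CR with no later confirming scan becomes a confirmed PR, while Table 14-1 read with consecutive scans gives SD

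*SAP*

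**What the plan says.** SAP Section 5 and Protocol 8.2.2 both require a CR or PR to be confirmed on a repeat assessment that is *consecutive* and at least four weeks later. SAP Section 5 defines ORR as the share of subjects whose BOR is CR or PR, and refers to Appendix B for the derivation of BOR.

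In Appendix B, Table 14-1 "provides the BOR determination per RECIST 1.1 for trials where response confirmation is required", and a BOR taken from it is called the Confirmed_BOR. The text explains that "a confirmation is required by a repeat assessment at least 4 weeks after the first detection and assessments of NE may occur" between T1 and T2, and the table footnote repeats this: "Notice an unlimited number of intermittent assessments of NE can occur between the initial response and the confirmation". No other category is named as allowed in between. A NON-CR/NON-PD timepoint counts as SD.

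Table 14-2 then sets out the steps for deriving the same Confirmed_BOR. Step ii(a), for a current CR or PR, reads: "Find last scan that is not NE or SD and at least 28 days before current visit". Step ii(b) reads: "If none of above fits, find last scan that is not NE", and then refers to Table 14-1. Step iii keeps the better of the new result and the previous one.

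SAP Section 10 states that nothing departs from the protocol's analyses.

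**The concern.** The two tables are meant to give one answer, but the look-back in step ii(a) ignores SD as well as NE. A first PR and a later PR or CR can therefore confirm each other across an SD scan, which the consecutive rule does not allow.

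The result feeds straight into what is reported. The RECIST 1.1 BOR distribution and the ORR with its 95% CI, by planned dose level, are the only efficacy results that SAP 9.5.2 tabulates. The same subject would be a responder under the programming steps and a non-responder under the SAP's own definition, and SAP Section 10 would not disclose it.

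**Working it through.** **Inputs.** Scan days come from Protocol Table 1-3: every 6 weeks to week 12, then every 8 weeks, which gives days 42, 84, 140 and 196. The rules are rows C5, C11, C13, C15 and C21 of Table 14-1 and steps i to iii of Table 14-2. Assumption: T2 is the next evaluable scan, with NE passed over.

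**PR-SD-PR, no further scan**

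| Scan | Table 14-1 with this scan as T1 | Table 14-2 step at this visit | Confirmed_BOR, Table 14-2 |
|---|---|---|---|
| Day 42: PR | C13 (PR then SD): SD | i, using C15: SD | SD |
| Day 84: SD | C21 (SD then any): SD | ii(b), using C13: SD | SD |
| Day 140: PR | C15 (PR, nothing after): SD | ii(a) skips day 84 and pairs with day 42; 140 − 42 = 98 days, at least 28: PR | PR |

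The best result from Table 14-1 is SD. Table 14-2 ends at PR, and step iii keeps it.

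**PR-SD-CR, no further scan.** Table 14-1 gives C13, C21 and C5, all SD. At day 140, step ii(a) pairs CR with the earlier PR and returns PR.

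**Where the tables agree.** PR-SD alone is SD in both. PR-NE-PR is PR in both. PR-SD-PR-PR is PR in both, because the last two scans confirm each other (C11).

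**All histories on the planned days.** These counts cover sequences of CR, PR, SD and NE, leaving out those that Table 14-1 sends to query. They count patterns and are not probabilities.
- Three scans: 4³ = 64 sequences, of which 18 go to query, leaving 46. The tables differ on 2 (PR-SD-PR and PR-SD-CR).
- Four scans: 146 remain, and the tables differ on 13.
- Every difference is SD in Table 14-1 and PR in Table 14-2.
- If an intervening SD breaks confirmation in step ii(a), 0 differ.

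**Size per affected subject.** The SAP's own precision figure reproduces first: 7/36 = 19.4%, Clopper-Pearson 95% CI 8.2% to 36.0%, against the stated 19% and 8% to 36%. Each affected subject adds 1/n to ORR:

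| n | Without | With one such subject |
|---|---|---|
| 36 | 7/36 = 19.4% (8.2 to 36.0%) | 8/36 = 22.2% (10.1 to 39.2%) |
| 6 | 0/6 = 0% (0 to 45.9%) | 1/6 = 16.7% (0.4 to 64.1%) |
| 4 | 0/4 = 0% (0 to 60.2%) | 1/4 = 25% (0.6 to 80.6%) |
| 3 | 0/3 = 0% (0 to 70.8%) | 1/3 = 33.3% (0.8 to 90.6%) |

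The small denominators may be nearer the case, since results are tabulated by dose level and SAP 7.1 records early termination. The SAP does not give the number enrolled.

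**The case against.** **T2 is undefined.** Table 14-1 works on pairs of timepoints and never says how T2 is chosen. If T2 could be any later scan, the PR at week 6 and the PR at week 20 would satisfy C11 and give PR. Appendix B says that NE may occur in between; it does not say that only NE may. This stands in part: the SD result depends on a reading. That reading has the better support, because SAP Section 5 and Protocol 8.2.2 both use the word *consecutive*, and a later scan with an SD before it is hard to call consecutive.

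**Skipping SD may be deliberate.** Step ii(a) excludes NE and SD, while step ii(b) excludes only NE, which looks like a choice. A sum of diameters moving between −31%, −29% and −31% would read PR-SD-PR without any real loss of response. This is fair, but if it is the intention the SAP does not state it, and the other provisions would have to change to match. A reader might also infer an intention to inflate ORR; nothing in the documents supports that.

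**CR-SD-CR.** A reader might infer that step ii(a) simply turns this history into a confirmed CR. It does not. At visit 2 the current scan is SD, so step ii(b) applies and leads to the query in row C3, as Table 14-1 does. The footnote then foresees two outcomes. If the CR was real, the later disease is progression and "Best overall response would depend on whether minimum duration for SD was met"; otherwise "the original CR should be changed to PR and the best response is PR". A confirmed CR would follow only if the query left all three scans unchanged.

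**Small effect.** The history needs a response, an intervening SD, a regained response at least 28 days after the first, and no later confirmation. ORR is secondary and untested, and Protocol 9.4.2.2 plans listings in which such a subject could be seen. All of this stands and limits the weight of the point.

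**Conclusion.** The point holds for PR-SD-PR and PR-SD-CR, and for longer histories of the same kind, where no later scan confirms the regained response. Step ii(a) makes these a confirmed PR. Table 14-1 makes them SD when T2 is the next evaluable scan, the reading that follows from the consecutive rule in SAP Section 5 and Protocol 8.2.2. Relative to that reading the step can only raise ORR.

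The documents do not support a claim that the reported ORR is biased by any given amount. They give no frequency for these histories, and the effect is zero if no subject has one. The table of sizes is an illustration for one subject.

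A separate and lesser gap concerns unscheduled scans, of which the Table 14-1 footnote says: "Both first detection and repeat assessment can be unscheduled visit and the 4 weeks apart rule needs to be met". With scans on days 42, 56 and 77, PR-PR-PR is SD in Table 14-1 (14 and 21 days to the next scan) but PR in Table 14-2 (77 − 42 = 35 days). That difference does not come from skipping SD.

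**What to change.** Reconcile the two tables before the final outputs are produced.

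**To keep the consecutive rule**
1. Reword step ii(a): *Find the most recent CR or PR scan at least 28 days before the current visit such that all scans between it and the current visit are NE, CR or PR; any intervening SD or PD breaks confirmation.*
2. State above Table 14-1 that T2 is the next evaluable scan.
3. Check the program on PR-SD-PR (SD), PR-SD-CR (SD), PR-NE-PR (PR) and PR-SD-PR-PR (PR).

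**If an intervening SD is meant to be allowed**, amend Table 14-1, the two NE sentences in Appendix B and SAP Section 5, and declare the departure from Protocol 8.2.2 in SAP Section 10.

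**Optional and secondary:** state how T2 is chosen when unscheduled scans fall less than 28 days apart.

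The cost of keeping the consecutive rule is a short SAP edit and one program condition, with no new data. ORR may be lower or unchanged.
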